Not useful 17.2 HCP Checklist rograming Note: if response to Q11 or (Not Som useful us 17.3 Patient Alert	Somewhat useful Q12 is YES, the newhat	No opinion/not sure 	Very useful	Extremely useful
useful 17.2 HCP Checklist rograming Note: if response to Q11 or Q Not Som useful us 17.3 Patient Alert	useful Q12 is YES, the newhat	opinion/not sure	useful	useful
rograming Note: if response to Q11 or	Q12 is YES, the	hey can continu		
Not Som useful us	iewhat]		ie with Q	17.3
useful us 17.3 Patient Alert		NI. X7		
	-	No Ver nion/not usef sure	•	remely seful
Which precautionary measures d prescribe VFEND (voriconazole))? Please check			or whom you
Avoiding exposure to dire		taviaity		
Detecting signs and symptUse with caution in patien	•	•	testinal u	lceration or
diverticulitis	•	•		
Dermatologic evaluation s basis	hould be perfo	formed on a syst	tematic ar	nd regular

	Covering sun exposed areas of skin		
	Use sufficient sunscreen with high sun protect	ion factor (SPF)	
	Clinical signs of liver damage, such as jaundic doctor immediately	e that warrant con	tacting the
	International Normalized Ratio regular monitor	oring	
	Avoid invasive dental procedures		
	Note: if response to Q11 or Q12 is YES, they can tents of the Patient Alert Card" in Q18a	n continue with op	otions
18a.	Do you, or another member of your healthcar other) perform each of these activities when it VFEND (voriconazole)? (Please check one rebelow).	nitiating treatment	with
		Yes	No
	Discuss contents of the Patient Alert Card		
	Advise patient to avoid exposure to direct sunlight and/or to use measures such as protective clothing and sunscreen		
	Discuss risk of lymphoma		
	Discuss risk of gastric perforation		
	Advise patient of importance of monitoring risks of VFEND (voriconazole) use and signs and symptoms of serious risks that warrant contacting doctor immediately		
	Discuss risk of amyloidosis		
19. How	frequently do you perform Liver Function Tests	s (specifically AST	T, ALT)?
	At VFEND (voriconazole) treatment initiation month	and weekly therea	after for one
	At every contact		
	Monthly		

		Other [Free text] I do not know
20.	of VI	ere are no changes in Liver Function Tests (LFTs) after one month of initiation FEND (voriconazole), how often do you monitor liver function during VFEND ment maintenance?
		Weekly
		Monthly
		Other [Free text]
		I do not know
21.		often do you perform a dermatologic evaluation when VFEND (voriconazole) ntinuously used despite the occurrence of phototoxicity-related lesions? Weekly Monthly Every two months
		On systemic and regular basis
		I do not know
22.		which of below condition(s) would you discontinue VFEND (voriconazole) in a nt? (Select the one best response).
		Phototoxicity
		Squamous Cell Carcinoma (SCC)
		Premalignant lesions
		All of the above

23. Did you or another staff member request additional copies of the VFEND (voriconazole) RM tools?

Redacted

Voriconazole A1501110 NON Version 1.0, 16	-INTERVENTIONAL STUDY PROTOCOL August 2024
	Yes
	No
[CLOSING	
	Thank you.

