7. RATIONALE AND BACKGROUND

Voriconazole (Vfend®) is a broad spectrum triazole antifungal agent used in the treatment of a range of serious fungal infections in both inpatient and outpatient settings. The clinical benefit of voriconazole has been demonstrated for the treatment of invasive aspergillosis (IA), candidemia in non-neutropenic patients, fluconazole-resistant serious invasive Candida infections (including *Candida krusei*), and serious fungal infections caused by *Scedosporium* spp. and *Fusarium* spp. for which voriconazole is authorised for use in the Saudi Arabia. Voriconazole is also indicated in Saudi Arabia for the prophylaxis of invasive fungal infections in high risk allogeneic hematopoietic stem cell transplant (HSCT) recipients.

Phototoxicity, squamous cell carcinoma (SCC) of the skin, and hepatic toxicity have been designated as important 'identified' risks with administration of voriconazole in the Risk Management Plan (RMP) and are currently described in the Summary of Product Characteristics (SPC). To ensure that these risks are adequately managed, additional risk minimisation measures (aRMMs) across Saudi Arabia have been implemented in February 2023. These included updating the voriconazole SPC¹ with revisions to information on hepatotoxicity, phototoxicity, and SCC of the skin (routine risk minimisation activity), and developing a comprehensive educational programme at the point of patient care, intended to educate/remind healthcare professionals (HCPs) about the risks and how to manage them. These aRMMs target specialty care physicians who prescribe voriconazole (i.e., infectious disease physicians), and clinical pharmacists who manage the drug and its interactions (hereafter referred to as "HCPs"). The details of the Risk Minimisation (RM) tools for the education programme and how these tools are being implemented in Saudi Arabia are described in the RMP. The three components of the RM tools are the HCP Checklist, HCP Question & Answer (Q&A) Brochure, and Patient Alert Card. A brief description of each follows:

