Knowledge about the RM tools	Q7. According to the SPC/PI, the known risks for VFEND (voriconazole) are as follows: (Please select only one response for each of the risks listed in the table below.) Q8. Please select only one response for each statement about VFEND	Yes	Question completed correctly (6 points) Question completed correctly (5 points)	An HCP is considered successful for Knowledge when he/she provides at least 9 out of 11 (~80%) correct/desirable responses. Success for
Self-declared behavior/ Practice	(voriconazole) below: Q18. Which precautionary measures do you communicate to your patients for whom you	Yes	Question completed desirably (6 points)	Knowledge: if ≥80% of HCPs are successful An HCP is considered successful for awareness when he/she provides
	prescribe VFEND (voriconazole)? Please check all that apply. 18.a Do you, or another member of your healthcare team (e.g., nurse, pharmacist or other) perform each of these activities when initiating treatment with VFEND (voriconazole)? (Please check one response for each activity below).	Yes	Question completed desirably (6 points)	desirable responses to all sub-questions. Success for self-reported practices if ≥80% of HCPs are successful
	Q19. How frequently do you perform Liver Function Tests (specifically AST, ALT)?	Yes	Question completed desirably (Answer 1 is desirable)	

Q20. If there are no changes in Liver Function Tests (LFTs) after one month of initiation of VFEND (voriconazole), how often do you monitor liver function during VFEND treatment maintenance?	Yes	Question completed desirably (Answer 2 is desirable)	
Q21. How often do you perform a dermatologic evaluation when VFEND (voriconazole) is continuously used despite the occurrence of phototoxicity related lesions?	Yes	Question completed desirably (Answer 4 is desirable)	
Q22. For which of below condition(s) would you discontinue VFEND (voriconazole) in a patient? (Select the one best response).	Yes	Question completed desirably (Answer 4 is desirable)	

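### Three decoy rows in Q18a do not name voriconazole as the cause of the risk, so a truthful Yes given for another reason would fail an HCP on the all-or-nothing practice score

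*Protocol*

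**What the plan says.** Q18a (Annex 1.2) asks whether the respondent, or a colleague on the healthcare team, does the following: "perform each of these activities when initiating treatment with VFEND (voriconazole"). Each of six rows is answered Yes or No. Three rows match the messages of the risk minimisation tools described in Section 7: going through the Patient Alert Card, advising on sun protection, and advising on monitoring and warning signs. The last of these names the drug, since it refers to "risks of VFEND (voriconazole) use and signs and symptoms of serious risks that warrant contacting doctor immediately".

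The other three rows are "Discuss risk of lymphoma", "Discuss risk of gastric perforation" and "Discuss risk of amyloidosis". They name a risk but not its cause.

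Annex 1.5 counts Q18a towards success and describes its scoring only as "Question completed desirably (6 points"). An HCP succeeds on practice by giving "desirable responses to all sub-questions", and the objective succeeds if at least 80% of HCPs do so. Section 9.1 aims for 10 completed surveys. Objective 4 (Section 8) concerns practices that minimise three risks in line with the SPC: phototoxicity, SCC of the skin and hepatic toxicity.

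**The concern.** The stem fixes the occasion (starting voriconazole) but not the reason for the discussion. A Yes to a decoy row can mean two things. The team may wrongly present the risk as one of the drug, or it may raise the topic at the same visit for an unrelated reason. Only the first bears on objective 4, yet both would be scored the same way. Because the question also covers colleagues, a truthful Yes need not reflect the respondent's own counselling.

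The two meanings cannot be separated afterwards. Answers are Yes or No only, every question is compulsory (Section 9.9.2), earlier answers cannot be changed (Section 9.9.1), and respondents will not be queried (Section 9.6). No later analysis plan can recover the reason for a Yes. With no error allowed on any practice item, one such answer cancels an otherwise perfect practice score.

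**Working it through.** **1. Are the decoy rows scored?** Annex 1.5 gives no row-level key for Q18a, so this has to be inferred from the points.

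| Item | Rows or options | Matching the tools or SPC messages | Points in Annex 1.5 |
|---|---|---|---|
| Q7 | 6 | 3 | 6 |
| Q8 | 5 | all five are true/false statements | 5 |
| Q18 | 9 | 6 | 6 |
| Q18a | 6 | 3 | 6 |

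Q7 and Q8 reproduce the plan's own total: 6 + 5 = 11. The pass mark of nine is 9/11 = 81.8%, which the plan gives as about 80%. Q7 therefore scores its decoys. In Q18 the 6 points can be reached from the matching options alone. If Q18a were scored on its matching rows alone, it would carry 3 points. It carries 6, so the three decoys must be scored. Given objective 4, the only sensible desirable answer to them is No.

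**2. Effect on one HCP.** One Yes to a decoy leaves at most 6 − 1 = 5 of 6 on Q18a. All practice sub-questions must be desirable, so that HCP fails on practice. The knowledge score, by contrast, tolerates 11 − 9 = 2 errors.

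**3. Effect on the objective.** With 10 HCPs, the threshold is 0.80 × 10 = 8 successes. Two affected HCPs leave 8/10 = 80%, which still passes. Three leave 7/10 = 70%, which does not.

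**4. Sensitivity.** Let p be the probability that an otherwise perfect HCP truthfully answers Yes to at least one decoy. The documents give no value for p, so it is assumed over a range. With X ~ Bin(10, p), the chance of meeting the threshold is P(X ≤ 2) = P(0) + P(1) + P(2):

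- p = 0.10: 0.3487 + 0.3874 + 0.1937 = 0.930
- p = 0.20: 0.1074 + 0.2684 + 0.3020 = 0.678
- p = 0.30: 0.0282 + 0.1211 + 0.2335 = 0.383

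With p = 0 the chance is 1.

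**5. Wording side by side.** The stem of Q7 asks about known risks of voriconazole, so a Yes to one of its decoys is a wrong statement about the drug. The monitoring row in Q18a also names the drug. The three decoy rows in Q18a do neither.

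**The case against.** **The key is inferred.** Annex 1.5 prints desirable answers for Q19 to Q22 but not for the rows of Q18a, and Q18 shows that points need not equal options. The Patient Alert Card row also appears only if Q11 or Q12 is Yes, so some HCPs see five rows. This stands as a caution. No = desirable remains the reading that best fits 6 points, and the missing key is itself worth repairing.

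**The context points to the drug.** The stem refers to starting VFEND, the survey is titled as a VFEND survey, and Q18, just before, concerns patients prescribed it. Many respondents will probably read the decoys as intended. Section 9.9.1 also promises a clarity test, which might catch the wording. This lowers the likely frequency of the problem but does not remove the ambiguity.

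**Respondent mix.** A reader might infer that the item mainly measures the case mix of haematology, oncology and transplant services and so biases objective 4 downward there. The documents do not support that. Section 7 does list "prophylaxis of invasive fungal infections in high risk allogeneic hematopoietic stem cell transplant (HSCT) recipients" as an indication, and Q5 offers those specialties as answers. But Sections 7 and 9.7 name infectious disease physicians and pharmacists as the groups concerned. Nothing in the protocol says that patients are counselled on lymphoma, gastric perforation or amyloidosis because of their disease or co-treatment. Half of the rows in Q18a do ask directly about risk minimisation.

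**The figures are generic.** Any scored practice item would produce the same table under the all-or-nothing rule. That is correct: the figures show how sensitive the rule is, not how large this particular error will be.

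**Decoys have a use, and results are descriptive.** Section 9.9.2 names social desirability bias, and decoys help to detect indiscriminate Yes answers. There is no formal test (Section 9.5), and Section 9.7 reports responses to each practice question, so an anomaly in Q18a might be noticed. It could be noticed but not explained, because the reason for a Yes is not collected.

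**Conclusion.** The point holds as a wording and scoring defect in one item. Three rows of Q18a can draw a truthful answer that would be scored as undesirable without breaching objective 4, and the scoring rule gives that answer decisive weight for the HCP concerned.

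This rests on two inferences: that the three rows are decoys, because they match none of the tool messages in Section 7, and that No is their desirable answer, because the item carries 6 points for 6 rows.

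The size is unknown. Three affected HCPs out of 10 would suffice to miss 80%. The chances of 93%, 68% and 38% apply only if p is 10%, 20% or 30% and every other practice answer is desirable. A reader might infer that the objective is likely to fail because of this item, or that one Yes fails the objective itself. Neither follows: one Yes fails one HCP's practice score, and the documents give no rate from which a likelihood could be derived.

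**What to change.** Before the survey is programmed:

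- Reword the three decoy rows in Annex 1.2 so that they name the drug as the cause, for example *Tell the patient that lymphoma is a risk of VFEND*, and likewise for gastric perforation and amyloidosis.
- State in Annex 1.5 that No is the desirable answer to these three rows.

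This keeps the check on indiscriminate Yes answers and brings Q18a into line with Q7. The cost is slightly longer item text and one added line in the scoring table. Leaving the decoys unscored and reporting them descriptively would also remove the misclassification, but the score would then lose the check on yes-saying, so rewording is preferable.

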- HCP Checklist for the risks of phototoxicity, SCC of the skin and hepatic toxicity: This is the core RM tool that reminds HCPs about: i) the risks of phototoxicity, SCC of the skin, and hepatic toxicity with the use of voriconazole, ii) the appropriate use of voriconazole and management of patients with underlying hepatic impairment and those developing hepatic injury during voriconazole therapy as described in the SPC, iii) the dermatological examination and liver function monitoring required per the SPC, iv) discussing the importance of monitoring these risks with patients, and, v) providing the Patient Alert Card (described below) to each patient prescribed voriconazole. The HCPs have been instructed to complete the HCP Checklist for all new patients receiving voriconazole and retain it in the patient's medical record.
- HCP Q&A Brochure for the risks of phototoxicity, SCC of the skin and hepatic toxicity: This brochure in Q&A format provides detailed information to HCPs about: i) the risks of phototoxicity, ii) counselling patients regarding the risks of hepatotoxicity and SCC of the skin, iii) alerting patients/caregivers to the signs and symptoms that warrant contacting the doctor immediately, iv) regular dermatological examination and liver function monitoring as described in the SPC, v) discontinuing voriconazole if premalignant lesions or SCC are identified; and, vi) providing the Patient Alert Card to patients prescribed voriconazole. This brochure also provides information about the HCP Checklist and Patient Alert Card and instructs HCPs how to use these tools when managing patients receiving voriconazole.
- Patient Alert Card for the risks of phototoxicity and SCC of the skin: The purpose of this wallet-sized folded card is to help remind patients about the need for dermatological evaluations on a regular basis (if phototoxic reactions occur). It also prompts the patient to report phototoxic symptoms that increase the risk of SCC of the skin. Furthermore, patients are reminded to avoid exposure to sunlight, to use protective clothing and sunscreen with high sun protective factor (SPF), and to inform their physicians if they develop sunburn or severe skin reactions or skin abnormalities. The HCPs were instructed to fill in their contact details on the card and give a card to each patient undergoing treatment with voriconazole.

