All questions must be answered in order to complete the survey. In each survey, response options presented in a list will be presented in random order (where appropriate) to minimise positional bias. Programming will be reviewed by quality control and simulated users (User Acceptance Testing) prior to implementing the survey.

2. Generalization of the survey results to the overall target population

In such surveys, the generalization and external validity of the results is restricted to HCPs who can be reached and are willing (and able) to answer a questionnaire online questionnaire. These HCPs may not be fully representative of the whole target population.

The study report will discuss the results in the light of the limitations described above including variability and uncertainty of the data and methods.

Redacted

Finally, the marketing authorization holder (MAH) acknowledges that an a priori threshold of 80% correct per risk questions will be used to define the success of the program. However as acknowledged by EMA, the selection of this threshold for success is subjective (7 May 2015 PRAC Rapporteur PASS Protocol Assessment Report; Procedure no.: EMEA/H/C/000387/MEA 087.2) and not based on a prior knowledge, experience, or established scientific criteria in the education or risk communication literature. The MAH expects that the knowledge may differ by key risk message, clinical practice, & HCP specialties. Moreover, sample size may not be sufficient to conduct subgroup or stratified analyses.

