- VFEND has been associated with phototoxicity and pseudoporphyria. It is recommended that all patients, including children, avoid exposure to direct sunlight during VFEND treatment and use measures such as protective clothing and sufficient sunscreen with high sun protection factor (SPF).
- The frequency of phototoxicity reactions is higher in the paediatric population. As an evolution towards SCC has been reported, stringent measures for the photoprotection are warranted in this population of patients. In children experiencing photoaging injuries such as lentigines or ephelides, sun avoidance and dermatologic follow-up are recommended even after treatment discontinuation.
- Squamous cell carcinoma (SCC) of the skin has been reported in patients taking VFEND, some of whom have reported prior phototoxic reactions.
- If phototoxic reactions occur, multidisciplinary advice (e.g. a consultation with a dermatologist) should be sought
 for the patient. VFEND discontinuation and use of alternative antifungal agents should be considered.
- Dermatologic evaluation should be performed on a regular basis whenever VFEND is continued, despite
 occurrence of phototoxicity-related lesions to allow early detection and management of premalignant lesions.
- VFEND should be discontinued if premalignant skin lesions or skin SCC are identified.
- SCC has been reported in relation with long-term VFEND treatment. Treatment duration should be as short as
 possible. Long- term exposure (treatment or prophylaxis) greater than 180 days (6 months) requires
 careful assessment of the benefit risk balance and physicians should therefore consider the need to limit
 the exposure to VFEND.
- For prophylaxis use, dose adjustments are not recommended in the case of lack of efficacy or treatment-related
 adverse events. In the case of treatment-related adverse events, discontinuation of VFEND and use of
 alternative antifungal agents must be considered.

Refer to the Summary of Product Characteristics for full prescribing and adverse event information.

Please review and answer the questions below for each patient receiving	og VEEND:
△ Has your patient developed phototoxicity? If YES, please refer to the Summary of Product Characteristics (SmP	YES NO
△ Have you arranged regular dermatologic evaluation for the patient presented with phototoxicity? If YES, please refer to the SmPC for further details. If NO, regular dermatologic evaluation should be arranged promptl details.	

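### Q21 scores weekly, monthly and two-monthly skin evaluation as undesirable, although each is a regular schedule, and apart from 'I do not know' offers no answer for irregular or absent evaluation

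*Protocol*

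**What the plan says.** Q21 (Protocol, Annex 1.2) asks how often the HCP performs a dermatologic evaluation when voriconazole is continued despite phototoxicity-related lesions. It has five options: "Weekly Monthly Every two months" (answers 1 to 3), "On systemic and regular basis" (answer 4) and 'I do not know' (answer 5). Annex 1.5 keys answer 4 alone as desirable. It counts an HCP as successful on practice only if all practice sub-questions are answered desirably, and the objective as met if at least 80% of HCPs succeed.

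The standard for dermatologic follow-up appears in several places:

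- Checklist page in Annex 1.2: "Dermatologic evaluation should be performed on a regular basis whenever VFEND is continued".
- YES/NO item on the same page: "Have you arranged regular dermatologic evaluation for the patient presented with phototoxicity".
- Brochure summary, Section 7: "regular dermatological examination and liver function monitoring as described in the SPC".
- Patient Alert Card summary, Section 7: "the need for dermatological evaluations on a regular basis (if phototoxic reactions occur".
- Q18 in Annex 1.2 lists evaluation on a systematic and regular basis as a precautionary measure.

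None of these names an interval. Q19 and Q20 offer "Other [Free text"; Q21 does not. Section 9.9.2 adds: "All questions must be answered in order to complete the survey".

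**The concern.** The options are not mutually exclusive. Weekly, monthly and two-monthly evaluation are all regular, so answers 1 to 3 are particular cases of answer 4, yet they are scored as failures. The question asks how often, and the key penalises the precise reply while rewarding the vague one.

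The item is also weak in the other direction. Apart from 'I do not know', nothing describes evaluation that is irregular, prompted only by symptoms, or not done. Such an HCP must still answer in order to submit, and one of the inaccurate choices is the keyed one.

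Endpoint 4 is the proportion of HCPs whose practice answers agree with the SPC. Under the all-items rule a single interval answer in Q21 removes an HCP from the numerator, whatever the other answers were.

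**Working it through.** **Classification.** Setting Q21 and its key beside the displayed standard:

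| HCP's actual practice | Meets the displayed 'regular' standard? | Option describing it | Scored in Annex 1.5 |
|---|---|---|---|
| Weekly, monthly or every two months | Yes | Answers 1–3, or equally answer 4 | Undesirable if 1–3, desirable if 4 |
| Regular, at another interval | Yes | Answer 4 | Desirable |
| Irregular, symptom-driven or none | No | None | Depends on which inaccurate option is picked |
| Does not know | Not established | Answer 5 | Undesirable |

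The first row is the false failure: the same HCP would tick YES on the Checklist item. The third row is the gap in the option list. The order of options agrees with the key, so the problem does not come from how the PDF was read.

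**Threshold.** Section 9.1 targets 10 completed surveys. At least 80% of 10 means at least 8 successful HCPs. Three HCPs who answer with an interval leave at most 7/10 = 70%, so the practice objective is missed even if all ten follow the displayed standard.

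**Illustration of size.** The protocol states no figure for this item, so there is none to reproduce. Two inputs have to be assumed:

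- f, the share of HCPs who tick one of answers 1 to 3 although their practice is regular; all others tick answer 4.
- q, the probability that an HCP is desirable on every other practice item, independent of f.

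The number of successful HCPs is then X ~ Bin(10, q(1 − f)), and the objective is met with probability P(X ≥ 8). The column f = 0 is what would result if regular intervals were accepted.

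| q | f = 0 | f = 0.1 | f = 0.2 | f = 0.3 | f = 0.5 |
|---|---|---|---|---|---|
| 1.0 | 1.00 | 0.93 | 0.68 | 0.38 | 0.055 |
| 0.9 | 0.93 | 0.71 | 0.44 | 0.22 | 0.027 |
| 0.8 | 0.68 | 0.44 | 0.24 | 0.11 | 0.012 |
| 0.7 | 0.38 | 0.22 | 0.11 | 0.048 | 0.005 |
| 0.5 | 0.055 | 0.027 | 0.012 | 0.005 | 0.0004 |

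Example: q = 0.9 and f = 0.2 give a success probability per HCP of 0.9 × 0.8 = 0.72, and P(X ≥ 8) = 0.44, against 0.93 at f = 0.

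How large q might be depends on the other 15 scored practice points (six in Q18, six in Q18a, and Q19, Q20 and Q22). If these were independent, 98% desirable per point would give q = 0.98^15 ≈ 0.74, and 95% would give 0.95^15 ≈ 0.46. The upper rows of the table therefore need very high performance on each item.

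**The case against.** Five arguments can be made for leaving the item alone.

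- **Answer 4 is not arbitrary.** Apart from 'systemic', probably a slip for 'systematic', it repeats the wording of Q18, and the intervals can be read as distractors. This explains the key but does not rescue it: a fixed weekly or monthly schedule is systematic as well as regular. Q21 also asks what the HCP does and is classed under practice, so it is not a test of recalling a phrase.
- **The SPC governs, and it is not in the documents.** Only page 1 of 3 of the Checklist is shown, the Brochure and Card are only summarised, and the Checklist summary in Section 7 gives no frequency at all. This is a real limit. If the SPC did name an interval, however, answer 4 alone would not express it and the key would still need changing.
- **Omitting free text is consistent with other sections.** Section 9.4 describes closed-ended questions, and Section 11 says there is no free-text field where safety information could be entered. That is fair, and the remedy needs no free text; the missing closed options remain.
- **The all-items rule with 10 HCPs is the larger driver.** At q = 0.5 the objective is almost certainly missed with or without Q21 (0.055 against 0.012 at f = 0.2). This stands and limits the effect of Q21 alone.
- **The consequence is softened.** There is no formal test, the 80% threshold is declared subjective, answers are reported item by item, and clarity testing is planned. A reader of the report could see the interval answers and reinterpret them. The pre-specified classification would still be wrong.

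**Conclusion.** The concern holds. Three of the five options fit the standard displayed in the protocol but are scored undesirable, and apart from 'I do not know' no option describes non-adherent practice. This is a fixed option list and key in the protocol's own annexes, to which Section 9.7 refers for the details of success, so it is not a detail left to the SAP.

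The firm part of the size is that three interval answers among 10 HCPs miss the criterion. The probabilities rest on assumed f and q and on their independence. On those assumptions Q21 matters most when the other practice items are mostly passed, and adds less in absolute terms at q = 0.7 or below. They show the effect of false failures only. Whether HCPs without a schedule would tick answer 4 is unknown, so the net direction of bias in endpoint 4 cannot be stated. The item should be corrected before use.

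**What to change.** Before the survey is programmed, replace the Q21 options with mutually exclusive ones:

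1. At regular intervals
2. Only when lesions change or the patient complains
3. Not done
4. I do not know

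Key the first as desirable in Annex 1.5, and ask those who choose it for the interval as an unscored, closed follow-up. The first option may attract socially desirable answers, a bias Section 9.9.2 already acknowledges, but HCPs without a schedule would at least have an accurate choice. If the SPC does name an interval, key to that instead.

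A fallback is to keep the present options and key answers 1 to 4 as desirable. This removes the false failures but leaves 'I do not know' as the only failing answer, so the item would not detect non-adherence.

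The cost is one reworded question with its follow-up, one key cell, and a version update of Annexes 1.2 and 1.5. The abstract ties the timeline to SFDA endorsement of the protocol, so the change should be made before endorsement or notified to the authority.
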